### 3.2.5 Exploratory Variables

CCI [REDACTED]

## 4 STATISTICAL METHODS

### 4.1 Data Quality Assurance

Tables/Figures/Listings (TFLs) to be included in the report will be independently checked for consistency, integrity and in accordance with standard Parexel procedures (SOP).

## 4.2 General Presentation Considerations

All tables, listings, and graphs will be produced to landscape orientation using Courier New 9pt font and will be incorporated into a MS Word document as a rich text file (RTF) (margins on standard A4: Margins (top, left, right, and bottom) 2.54 cm.

### 4.2.1 Study Days

Screening will be conducted between Day -28 and Day -1. The first day of treatment will be Cycle 0 - Day 1 (C0D1). When calculating AEs/ConMeds/etc timing days will be calculated relative to Day 1.

### 4.2.2 Visit Windowing

By visit summaries will be made considering the windows as below. The visit windowing is assessed relative to C1D1 date (not C0D1 due to delays between C0D1 and C1D1).

C0D1	C0D1
C1D1	(C1D1 - Day 8)
Day 15	(Day 9 - day 18)
Day 22	(Day 19 - Day 32)
Day 43	(Day 33 - Day 53)
Day 64	(Day 54 - Day 74)
Day 85	(Day 75 - Day 95)
Day 106	(Day 96 - Day 116)
Day 127	(Day 117 - Day 137)
Day 148	(Day 138 - Day 158)
Day 169	(Day 159 - Day 179)
Day 190	(Day 180 - Day 200)
Day 211	(Day 201 - Day 221)
Day 232	(Day 222 - Day 242)
Day 253	(Day 243 - Day 263)
Day 274	(Day 264 - Day 284)
Day 295	(Day 285 - Day 305)
Day 316	(Day 306 - Day 326)
Day 337	(Day 327 - Day 347)
Day 358	(Day 348 - Day 368)

The following visits will not be remapped: Screening, IP Discontinuation, 30/90 Day Follow-up, Survival Follow-up.

In case several visits occur into the same windows the following rule is to be applied:

- For by-visit table, we will consider the mean of available assessments.
- For Shift table, we will consider either Minimum or Maximum available value depending on the direction.

#### **4.2.3 Definition of Baseline and Post-baseline Assessments**

A baseline assessment will be defined as the last assessment performed prior to the first dose of study treatment (C0D1). While many of these assessments will be performed on the day of the first dose, others will be performed during screening. If a patient is missing an assessment typically performed on the day of the first dose, screening values may be substituted as baseline.

#### **4.2.4 End of Study (EoS)**

A patient is considered to have completed the study if he/she has completed all phases of the study (including the last visit and the last scheduled assessment shown in the SoA) or withdraws consent whichever occurs first.

The EoS is defined as the date of the last visit of the last participant in the study or the last scheduled assessment shown in the SoA for the last participant in the study before the data cut off (DCO). The study data is planned to be analysed and reported based on all patient data at the primary completion data cut-off date (approximately 24 weeks after cycle 1 day 1 for the last patient in), or at the End of Study, whichever comes first.

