6.6 Access to Study Treatment after the End of the Study

Any patients still receiving investigational product at the time of the data cut off will be able to continue to receive investigational products within the current study while in the Investigator's opinion, deriving clinical benefits and not fulfilling the discontinuation criteria.

In Module 3, for those patients who are continuing on combination therapy with RXC004 and pembrolizumab, both agents can be administered until discontinuation criteria are met.

Patients who discontinue RXC004 may continue to receive pembrolizumab q6w alone. The continued access to pembrolizumab will end when a criterion for discontinuation is met or 18 doses of pembrolizumab (q6w dosing) have been administered (approximately 2 years), whichever is sooner.

Assessments will revert to standard of care for each individual site.

In Modules 1 and 2, patients will continue to be monitored for all SAEs up to 30 (+3) days after the last dose of RXC004 (i.e. patients treated with RXC004 monotherapy only).

In Module 3, patients will continue to be monitored for all AEs and Events of Clinical Interest for pembrolizumab up to 30 (+3) days after the last dose of RXC004 or pembrolizumab.

Follow-up for SAEs will continue for 30 (+3) days after the last dose of RXC004 and for 90 days after the last dose of pembrolizumab.

A paper form process will be used for AE, Events of Clinical Interest, and SAE reporting. All SAEs and overdoses will be reported until 30 days after last dose of RXC004 (Modules 1 and 2) or 90 days after the last dose of pembrolizumab (Module 3). All pregnancies will be reported up to 5 months after the last dose of the study drug(s).

The investigational product will be supplied to sites manually. The investigational product dispensation and reconciliation will be handled by the study team at each patient's visit. The investigational product accountability information must still be collected until all patients have completed treatment.

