9.4.1 General Considerations

The study data is planned to be analysed and reported based on all patient data at the primary completion data cut-off date (approximately 24 weeks after Cycle 1 Day 1 for the last patient in Modules 1 and 2, or 90 days after the last dose of pembrolizumab for the last subject in Module 3), or at the End of Study, whichever comes first. Depending on recruitment the data may be reported separately for each module. If reported together in one CSR the efficacy data will be presented separately for each module and not pooled. Baseline characteristics and safety data will be presented separately and selected data may be pooled, which will be detailed in the SAP.

All analyses, summaries and listings will be performed using SAS software (version 9.3 or higher). For categorical variables the frequency and percentage will be presented. For continuous variables, the sample size (n), mean, median, and standard deviation, as well as the minimum and maximum values will be presented. Missing data will not be imputed unless otherwise stated.

A baseline assessment will be defined as the last assessment performed prior to the first dose of study treatment. While many of these assessments will be performed on the day of the first dose, others will be performed during screening. If a patient is missing an assessment typically performed on the day of the first dose, screening values may be substituted as baseline.

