## 1 INTRODUCTION

The analyses described in this statistical analysis plan (SAP) are based upon the following study documents:

- Study Protocol, Version 6 (04-Jan-2023)
- electronic Case Report Form (eCRF), Version 4.0 (01-Aug-2022)

The structure and content are based upon International Conference on Harmonization (ICH) requirements as detailed in ICH E3 – Structure and Content of Clinical Study Reports.

CCI  
CCI [REDACTED]

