### 3 INVESTIGATIONAL PLAN

#### 3.1 Overall Study Design and Plan

[figure not shown]
This is Phase II, modular, open label, multicentre, study to evaluate the preliminary efficacy and safety of RXC004 monotherapy in advanced solid tumours that have progressed following standard of care treatment.

The study initially opened with ring finger protein 43 (RNF43) loss of function (LoF) mutation-positive pancreatic ductal adenocarcinoma (PDAC) (Module 1) and biliary tract cancers (BTC) (Module 2). The purpose of Module 3 is to evaluate RXC004 1.5 mg in combination with pembrolizumab in patients with BTC. [CC1] [REDACTED] evaluable patients will be enrolled in each module.

The primary objective of the study is to assess the preliminary efficacy of RXC004 in each module in terms of progression free survival (PFS) at 6 months. Tumour assessment will be performed by Investigators every 6 weeks  $\pm$  1 week (relative to the date of initiation of study treatment) for the first 54 weeks, followed by q12w  $\pm$  1 week until radiological disease progression (as defined by Response Evaluation Criteria in Solid Tumours, version 1.1 [RECIST 1.1]). Following radiological progression, patients will be followed-up for safety and survival.

The general study design is summarized in [Figure 1](#).

Figure 1 - Overall Design

DCR, disease control rate; CCI [REDACTED] ECOG performance status, LoF, Loss of Function, ORR objective response rate; OS Overall survival; PFS progression free survival; KP Kamofsky performance status; RNF43 Ring finger 43; RXC004 Porcupine inhibitor.

The analyses will be conducted independently for each module. The module data will be locked before their analyses. All the populations and endpoints described hereafter must be considered independently for each module.

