#### 4.12.1 Adverse Events

Adverse Events will be collected from time of signature of informed consent form throughout the treatment period and until 30 days after the last dose of RXC004.

SAEs will be recorded from the time of signing of main study informed consent form until the follow-up period is completed: 30 days after the last dose of RXC004 for patients treated with RXC004 monotherapy only) or 90 days after the last dose of Pembrolizumab (for patients treated with RXC004 and Pembrolizumab).

The following variables will be collected for each AE:

- AE (verbatim)
- Start/Stop date
- NCI CTCAE grade at onset and grade changes
- Seriousness
- Investigator causality rating against the Investigational Product(s)
- Action taken with regard to Investigational Product(s)
- Action taken with regards to AE
- Outcome

In addition, the following variables will be collected for SAEs:

- Date AE met criteria for SAE
- Date Investigator became aware of SAE

- Death
- Hospitalisation
- Life threatening
- Congenital anomaly or birth defect
- Disability or permanent damage
- Other medically important serious event
- Date of hospitalisation
- Date of discharge
- Causality assessment in relation to study procedure(s)
- Causality assessment to other medication

Partially complete AE dates will not be imputed in the listings and the available day, month and year components will be used to determine if an adverse event is treatment-emergent taking the first dosing date and last treatment date as references.

More specifically:

- Start date of AE missing: Assumed to be date of first treatment dose.
- Start day and month of AE missing: Assumed to be date of first treatment dose (if same year for both dates), January first otherwise.
- Start day of AE missing: Assumed to be date of first treatment dose (if same month and year for both dates), first day of the month otherwise.
- End date for non-ongoing AE missing: Assumed to date of last treatment dose
- End day and month for non-ongoing AE missing: Assumed to be date of last treatment dose (if same year for both dates), December 31st otherwise.
- End day for non-ongoing AE missing: Assumed to be date of last treatment dose (if same month and year for both dates), last day of the month otherwise.

Treatment-emergent adverse events (TEAEs) with missing relationship to the study drug will be considered as related.

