#### 4.16 Changes in the Conduct of the Study or Planned Analysis

After an ongoing review of the available data the following changes to the final outputs were made compared to the protocol:

- Medical History will not be summarized but will be listed.
- CCI
- Overall Survival will not be summarized but will be listed.

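### SAP 4.2.4 omits the protocol's separate Module 3 data cut-off, so some 90-day post-pembrolizumab safety windows may still be open when the data are analysed

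*SAP*

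**What the plan says.** Protocol 9.4.1 gives two primary-completion cut-offs. The first is "approximately 24 weeks after Cycle 1 Day 1 for the last patient in Modules 1 and 2". The second is "or 90 days after the last dose of pembrolizumab for the last subject in Module 3". End of Study applies instead if it is earlier.

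SAP 4.2.4 has the corresponding sentence with only the first rule and no module named: "approximately 24 weeks after cycle 1 day 1 for the last patient in), or at the End of Study, whichever comes first".

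The SAP is meant to cover Module 3. Its Introduction names its source as "Study Protocol, Version 6 (04-Jan-2023"), a version that contains Module 3, and SAP 3.1 states that "All the populations and endpoints described hereafter must be considered independently for each module". SAP 4.16, introduced by "the following changes to the final outputs were made compared to the protocol", shows no change of cut-off in its visible bullets; one bullet is redacted.

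Three other places bear on the consequence:
- SAP 4.12.1 records SAEs in Module 3 until "90 days after the last dose of Pembrolizumab (for patients treated with RXC004 and Pembrolizumab"). The same section collects AEs, and defines TEAEs, only to 30 days after RXC004, for every module.
- Protocol 8.3.1 and 9.4.3.1 run the Module 3 AE and TEAE windows to 90 days after pembrolizumab, or to 30 days after it if new anticancer therapy starts.
- Protocol 6.6, on patients still receiving study drug at the cut-off, says: "A paper form process will be used for AE, Events of Clinical Interest, and SAE reporting".

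**The concern.** The cut-off decides which Module 3 safety data reach the tables. The protocol's rule is tied to the end of pembrolizumab follow-up. The SAP's rule is tied to enrolment and takes no account of how long a patient stays on treatment. The patients most exposed to truncation are those who remain longest on the combination.

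This matters more here than in a routine data cut. Protocol 12.3.1 says RXC004 has not been given with pembrolizumab before, and Appendix L 1 warns that immune-related events can appear months after the last pembrolizumab dose. For patients still treated at the cut, later events go onto paper forms, and neither document says that those reports will enter the SAP's tables.

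**Working it through.** The cut-off is a design rule, so the plan gives no statistical figure to reproduce. The check is calendar arithmetic, counting C1D1 of the last-enrolled patient as day 0.

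**Inputs**
- SAP cut (4.2.4): 24 × 7 = day 168.
- Pembrolizumab every 6 weeks from C1D1, ± 3 days (protocol 12.7.1, Table 18): dose k falls on day 42(k − 1).
- At most 18 doses (protocol 7.1).
- Window after the last dose: 90 days, or 30 days if new anticancer therapy starts (protocol 8.3.1, 9.4.3.1).

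**Latest last dose with a complete 90-day window:** 168 − 90 = day 78 (week 11.1). Doses 1 and 2 (days 0 and 42) qualify; dose 3 (day 84) does not.

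**Window end by last dose received:** 42(k − 1) + 90, or 42(k − 1) + 30 under the shortened rule.

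| Last dose | Given on day | 90-day window ends | Beyond day 168 by | 30-day window ends |
|---|---|---|---|---|
| 1 | 0 | 90 | closed | 30 |
| 2 | 42 | 132 | closed | 72 |
| 3 | 84 | 174 | 6 days | 114 |
| 4 | 126 | 216 | 48 days | 156 |
| 5 | 168 | 258 | 90 days | 198 |
| 18 | 714 | 804 | 636 days | 744 |

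If dose 3 is given 3 days early (day 81), its window ends on day 171, still after the cut. That shortfall is small against a cut described as approximate. From dose 4 it is not.

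**The SAP's own 30-day TEAE window:** 168 − 30 = day 138. A last-enrolled patient who stops RXC004 after day 138 has even this shorter window open at the cut.

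**Illustration of how common a third dose might be.** Time on treatment is not given, so I assume it is exponential with median m months of 30.4375 days. The fraction still treated at day d is then exp(−ln 2 × d / (30.4375 m)). I take m from 1.8 to 4.0. Protocol 2.2.4.4 gives median PFS of 1.8 and 2.0 months in the two pembrolizumab monotherapy studies in BTC, and protocol 11.5.1 gives 4 months for second-line chemotherapy.
- Day 84: 35% (m = 1.8), 38% (m = 2.0), 62% (m = 4.0).
- Day 168: 12% (m = 1.8) to 38% (m = 4.0).

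These are proportions of a hypothetical cohort, not a count of affected patients. The Module 3 sample size and the enrolment pattern are not available.

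**The case against.** The strongest reply is that this is carried-over text with modest consequences. SAP 3.1 likewise still describes 6-month PFS as the objective in every module. Several stronger readings that a reader might infer do fail:

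- **That the SAP contradicts itself.** It does not. SAP 4.12.1 sets how long SAEs are recorded per patient; 4.2.4 sets when data are cut. A cut often leaves recording windows open, and in Modules 1 and 2 it does so for patients still on drug. The conflict is between SAP and protocol.
- **That everyone with a third dose is truncated.** The 30-day rule closes the AE window after doses 3 and 4 on days 114 and 156.
- **That the SAP cut is always the earlier one.** The protocol's term, last subject, could mean last enrolled. If that patient has one or two doses, the protocol's cut is day 90 or 132, before day 168.
- **That moving the cut alone recovers late immune-related events.** The SAP's AE and SAE summary tables rest on TEAEs, which end 30 days after RXC004 stops. An event 60 days after both drugs stop would be missing from those tables under either cut and would appear, at most, in the all-AE listing.
- **That later events are lost.** Protocol 6.6 keeps SAE reporting to 90 days after pembrolizumab, and the SMC continues to review safety every 6 months. The section also concerns patients still on drug, and does not clearly extend the paper process to those already off it. The gap is in the analysis tables, not in pharmacovigilance.
- **That SAP 4.16 is silent.** With one bullet redacted, only its visible text can be called silent. Even if that bullet covers the cut-off, 4.2.4 would still need to agree with it.

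The omission of the protocol's Module 3 rule remains, and so does its effect on patients with open windows. The End of Study alternative does not help: the earlier date governs, so it can only bring the SAP cut forward.

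**Conclusion.** The point holds in a bounded form. SAP 4.2.4 does not carry the Module 3 cut-off in protocol 9.4.1, and no departure is visibly declared. At day 168 a last-enrolled Module 3 patient with three or more doses has an open 90-day window, by 6 days after dose 3, 48 days after dose 4 and up to 636 days after dose 18, unless the 30-day AE rule applies. Earlier-enrolled patients still on, or recently off, pembrolizumab at the cut are affected in the same way. Patients with one or two doses are not.

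Module 3 safety may therefore be under-reported relative to the protocol's follow-up. The documents do not show by how much. The result assumes dosing on schedule and reads the SAP cut as exactly 24 weeks. The mismatch should be corrected, together with the related one in the Module 3 AE collection period and TEAE definition.

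**What to change.** 1. In SAP 4.2.4, state the cut-off by module: the 24-week rule for Modules 1 and 2, and the protocol 9.4.1 rule for Module 3. Clarify that the last subject means the last to stop pembrolizumab, so that no window is open because of enrolment order.
2. If a 24-week ORR readout is wanted for Module 3, declare it in SAP 4.16 and produce the final Module 3 safety tables at the protocol cut-off.
3. In SAP 4.12.1, align the Module 3 AE collection period and TEAE definition with protocol 8.3.1 and 9.4.3.1: 90 days after pembrolizumab, or 30 days if new anticancer therapy starts. Without this, item 1 leaves late post-treatment events outside the TEAE-based tables.
4. Say whether events reported on paper after a cut enter the analysis database.

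The cost is a few lines of SAP text and, if an early ORR readout is kept, a second run of the Module 3 safety tables. The downside is later final safety reporting for Module 3: if a last-enrolled patient completed all 18 doses, the cut would fall on day 804 (about week 115) after that patient's C1D1, unless End of Study came first.

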#### **4.2.5 Data Listings**

All listings will include scheduled and unscheduled measurements. All listings will display the same number of decimals as in the source data. All raw data will be reported exactly as provided.

#### **4.2.6 Data summaries**

Summaries will be presented separately for module 1 and module 2&3.

#### **4.2.7 Figures**

Figures will be presented independently for each module.

#### **4.2.8 Handling of Dropouts or Missing Data**

There will be no imputation of missing data, unless otherwise stated.

#### **4.2.9 Analysis Conventions**

Continuous data will be summarized in terms of the mean, standard deviation, median, minimum, maximum and number of observations, unless otherwise stated.

The minimum and maximum will be reported to the same number of decimal places as the raw data recorded in the database. The mean, median, will be reported to one more decimal place than the raw data recorded in the database. The standard deviation will be reported to two more decimal places than the raw data recorded in the database. In general, the maximum number of decimal places reported shall be four for any summary statistic.

Categorical data will be summarized in terms of the number of patients providing data at the relevant time point (n), frequency counts and percentages. Any planned collapsing of categories will be detailed in the SAP text and the data displays.

Percentages will be presented to one decimal place. Percentages will not be presented for zero counts. Percentages will be calculated using n as the denominator.

Changes from baseline in categorical data will be summarized using shift tables where appropriate.

Confidence intervals will be presented to one more decimal place than the raw data.

#### 4.3 Software

TFLs and any non-descriptive statistical analysis will be produced using SAS® Software (Version 9.3 or higher). The REPORT procedure (SAS PROC REPORT) will be used to produce all table and listings; SAS/GRAFH will be used to produce all figures.

#### 4.4 Study Patients

A clear accounting of the disposition of all patients who enter the study will be provided from screening to study completion.

The following summaries will be provided:

- A summary of the number of patients who were screened (who signed main study ICF), who were exposed to study treatment, who completed the study or discontinued and primary reason for end of treatment will be summarized in the FAS.
- A summary of the patient disposition including the date the informed consent was signed, date of first/last intake of study drug and the primary reason for end of treatment will be listed.

A listing of patients included into each of the analysis set will be presented, related summary statistics will be provided. Patients who did not meet the eligibility criteria or were screen failures will also be listed.

#### 4.4.1 Protocol Deviations

Deviations from the protocol including violations of inclusion/exclusion criteria will be assessed as “minor” or “major” in cooperation with the Sponsor in an ongoing manner during protocol deviation review meetings. Major protocol deviations are defined as those deviations from the protocol likely to have an impact on the patient’s rights, safety, or well-being; and/or on the validity of the data for analysis. Protocol deviations are defined in the project-specific Protocol Deviation Specification. Whether a protocol deviation result in exclusion from a particular analysis set will be detailed in the protocol deviation specification and documented in the supporting protocol deviation review document.

The number and percentage of patients with major protocol deviations will be summarized by type of deviation for each Module in the FAS. The summary will be done separately for major protocol deviations leading to exclusion from the evaluable set and the other major protocol deviations. All protocol deviations will be listed.

